Adverse events will be monitored for 11 days following receipt of each dose of study vaccine. FRAs making daily home visits, as described above, will collect information on adverse events for all subjects. In addition, parent(s)/legal guardian(s) will be instructed to notify the Investigator should the subject develop any clinically significant illness or event, including but not limited to those requiring an unscheduled healthcare provider visit or prescription/non-prescription medications within 11 days (Days 0 to 10) of vaccination. All serious adverse events (SAEs) will be monitored from study enrolment to study completion. Details of the event, including concomitant medication(s) and treatment will be recorded on the SAE form provided.

If a subject terminates from the study due to an adverse event, the Investigator will report this to the Sponsor's pharmacovigilance group or designee, within 24 hours of learning of termination, by faxing the completed, signed and dated Subject Outcome page of the Case Report Form (CRF).

Table 3 summarises the study procedures for all subjects participating in the study. In order that study visits are scheduled within the correct timeframes, the day of study vaccination visit should be considered as Day 0.

Table 3

SCHEDULE OF PROCEDURES

Study Visits	1			2			3	
Visit Window (Days After Previous Visit)	(0)	(2-4)	(10-12)	(35±7)	(0)	(2-4)	(10-12)	(35±7)
Informed Consent	X							
Subject Eligibility	X							
Demography	X							
Medical History	X			◆				◆
Physical Examination	X							
Blood Sample	X			X				X
Vaccination	X			X				
Assess Acute Reactions – 15 Minutes Post Vaccination	X			X				
Daily home visits for complications and SAEs		X	X		X	X		
Review of Morbidity Data				X				X
Record Concomitant Medication Use	X			X				X
*Adverse Event Collection	X	X	X	X	X	X	X	X
Serious Adverse Event Reporting	X	X	X	X	X	X	X	X

Randomisation Procedures

A randomisation schedule will be prepared and provided by WLW or by their designate. Study participants will be prospectively randomised in a 1:1:1 proportion among Study Group 1, Study Group 2, and Study Group 3. See group distributions in Section 3.1.3. Once a subject number and/or treatment is assigned to a particular subject, it will not be reused, even if the subjects drops out of the study prior to administration of the first study vaccination.

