-- Administer assigned intranasal study treatment. The appropriate study personnel must update vaccine accountability records.

-- After vaccination, observe each subject for a minimum of 60 minutes. Emergency management supplies (AMBU bag, adrenaline [epinephrine], and antihistamines) will remain available for initial treatment of an allergic reaction if needed. Record any local reactions or systemic events on adverse event pages in the CRF.

-- Initiate home visits by the FRA as described above, beginning with the afternoon of the immunisation day.

-- The parent(s)/legal guardian(s) are asked to contact the FRA or field clinic immediately if any significant illness or hospitalisation occurs during the study period.

-- Any subject with a clinically significant event (e.g., high fever, convulsion, etc) should be evaluated immediately by a study physician.

-- Serious adverse events (SAEs) data, regardless of causality, will be collected up to study completion. All treatment and associated costs will be provided by the study, as described above.

-- Record all information in the appropriate source documents, and complete the CRF.

Study Visit Three, Study Termination

This visit occurs 35 (+/- 7) days after the second dose of assigned study vaccine. Surveillance staff will contact the parent/guardian and arrange for this visit to the clinic or arrange for the visit with blood collection to occur at home.

- Review subject data from the last visit.
- Obtain and record interim medical history since the last study visit (visit two). Obtain and record all adverse events and concomitant medications between Day 0 and Day 10 following second dose of assigned study treatment (see section 6.2).
- Collect approximately 5 ml of blood for immunogenicity testing.
- Serious adverse events (SAEs) data, regardless of causality, will be collected up to study completion. Any SAE ongoing at study termination must be followed until resolution.
- Record all information in the appropriate source documents, and complete the CRF.

VACCINE ADMINISTRATION

Vaccine to be Administered

At study Visit 1, each enrolled subject will receive either intranasal CAIV-T, or saline placebo, and may concomitantly receive OPV, as assigned. At Study Visit 2, the subject will receive the same intranasal study treatment that he/she received at Visit 1, but no oral treatment. The time interval between Dose 1 and Dose 2 will be 35 (+/- 7) days.

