Each of the six immune responses will be evaluated at level of 0.05. The overall level for the six tests remains <0.05 as the null hypotheses for the six tests are required to be rejected simultaneously in order to demonstrate the acceptability of responses of co-administration.

Subjects who were immunised per protocol with blood samples drawn per protocol will be included in the immunogenicity analysis. Specifically, subjects must meet the following criteria to be included in the immunogenicity analysis:

-- The first blood draw (Pre Dose 1) must have occurred at the day of the first dose but prior to the first dose.

-- Time interval between the first and second doses must be 35 + 7 days.

- The second blood draw (Post Dose 1) must have occurred at the day of the second dose but prior to the second dose.
- Time interval between the second dose and the third blood draw (Post Dose 2) must be 35 + 7 days.

Influenza Seronegative Baseline Population – defined for each influenza strain: Those subjects of the immunogenicity evaluable population who had baseline titres for serum A/H1N1, A/H3N2, or B HAI less than or equal to 1:4.

Immunogenicity All Available Population: Subjects who received at least one dose of the assigned treatment and had a pre-dose and post-dose evaluation of serum antibodies.

Safety Population: Subjects who received at least one dose of the assigned treatment.

The demographic data, including gender, and age at each dose, of the immunogenicity and safety analysis populations will be summarised. Baseline serum antibody levels will be reported and the subject definition for seronegative baseline will be applied as a grouping criterion for some immunogenicity outcome summaries.

The primary measure of immunogenicity will be:

- Poliovirus types 1, 2, and 3 by virus neutralisation assay;
- Influenza virus strains A/H3N2, A/H1N1, and B by hemagglutination inhibition assay (HAI). OPV immune response for each poliovirus type is measured at the end of study by 1:10 or greater virus neutralisation assay titre.

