CAIV-T immune response for each virus strain is measured at the end of study by an increase from baseline HAI of four-fold or greater. The primary endpoint for immunogenicity is the proportion of subjects achieving a post-vaccination serum antibody response (as defined above) for each antigen component of OPV and CAIV-T. The primary analysis interval for influenza strains A/H1N1, A/H3N2, and B is one month following the second intranasal vaccination. The primary analysis interval for poliovirus types 1, 2, and 3 is one month following the single dose of OPV.

The secondary endpoint for immunogenicity is the titre of serum antibody for each antigen component of OPV and the titre ratio to baseline of serum antibody to each virus strain of CAIV-T obtained 1 month after vaccination.

The primary analysis interval for influenza strains A/H1N1, A/H3N2, and B is one month following the second intranasal vaccination. The primary analysis interval for poliovirus types 1, 2, and 3 is one month following the single dose of OPV.

The safety objective is to assess the safety and tolerability of CAIV-T in healthy children aged 6 to less than 36 months.

The reactogenicity adverse events are:

Fever (axillary temperature > 37.5°C); Cough; Runny nose or nasal congestion; Irritability; Vomiting; Decreased activity; and Decreased appetite.

The proportion of subjects with any reactogenicity event reported and with other adverse events on any day during the 11-day period following each dose of CAIV-T or placebo will be evaluated. Serious adverse events occurring within 42 days of the first or second vaccination will be listed and summarised.

The overall incidence of reactogenicity events will be compared between the individual CAIV-T groups and the combined Placebo groups using two-sided Fisher's Exact Test. Exact 95% confidence intervals about reactogenicity adverse event frequency differences will be reported. The frequency of other adverse events will be separately compared between subjects randomised to CAIV-T or Placebo using two-sided Fisher's Exact Test.

Ethical Assurance for Protection of Human Rights

Describe in the space provided the justifications for conducting this research in human subjects. If the study needs observations on sick individuals, provide sufficient reasons for using them. Indicate how subject's rights are protected and if there is any benefit or risk to each subject of the study.

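### The Safety Population is defined by receipt of the assigned treatment, and other adverse events are compared by randomised group, so a mis-dosed child can be left out or counted under the wrong product

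*Protocol*

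**What the plan says.** All the governing text is in the protocol's Data Analysis section, except where noted.

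- Safety set: "Safety Population: Subjects who received at least one dose of the assigned treatment".
- The secondary immunogenicity set carries the same condition: "Immunogenicity All Available Population: Subjects who received at least one dose of the assigned treatment and had a pre-dose and post-dose evaluation of serum antibodies". The safety set therefore has no exposure rule of its own.
- Other adverse events: "The frequency of other adverse events will be separately compared between subjects randomised to CAIV-T or Placebo using two-sided Fisher's Exact Test".
- Reactogenicity and other adverse events are first summarised as proportions "on any day during the 11-day period following each dose of CAIV-T or placebo will be evaluated". That sentence names no population.
- Serious adverse events: "Serious adverse events occurring within 42 days of the first or second vaccination will be listed and summarised". Again no population is named. Under Research Design and Methods, "All serious adverse events (SAEs) will be monitored from study enrolment to study completion".
- Under Vaccine to be Administered, at Visit 2 "the subject will receive the same intranasal study treatment that he/she received at Visit 1, but no oral treatment".

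The regimens (Research Design and Methods) are:

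| Group | Dose 1 | Dose 2 |
|---|---|---|
| 1 | CAIV-T + OPV | CAIV-T |
| 2 | placebo + OPV | placebo |
| 3 | CAIV-T | CAIV-T |

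There are 800 children per group, 2,400 in all.

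**The concern.** A safety set normally holds every exposed child, grouped by what that child received. Here membership depends on a match between product and allocation, and the one comparison that states its grouping uses allocation. Two errors follow. A child exposed to the live investigational vaccine can fall outside the set. A child who stays inside can have events after CAIV-T counted as placebo events, or the reverse.

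The protocol makes a swap possible. CAIV-T and placebo sprayers are identically packaged, and staff are blinded to the intranasal product in Groups 1 and 2, so a swap between those groups need not be noticed on site. At stake is the third specific aim, the safety and tolerability of giving the two vaccines together to healthy children.

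**Working it through.** The protocol gives no figure on this point. Its sample-size calculation concerns immunogenicity and does not use the Safety Population. The first check is therefore to set the definition against the regimens.

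**1. Who is in the set if the whole course is swapped**

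| Assigned | Received | Any assigned product received? | In the Safety Population? | CAIV-T or placebo status wrong if grouped as randomised? |
|---|---|---|---|---|
| 2 | 3 | none | out | not applicable; child had CAIV-T |
| 3 | 2 | none | out | not applicable; child had placebo and OPV |
| 2 | 1 | OPV only | depends on whether OPV alone counts | yes, CAIV-T events under placebo |
| 1 | 2 | OPV only | depends on whether OPV alone counts | yes, placebo events under CAIV-T |
| 1 | 3 | CAIV-T | in | no |
| 3 | 1 | CAIV-T | in | no |

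Only swaps between Groups 2 and 3 exclude a child on every reading. Swaps between Groups 1 and 2, where blinding hides the error, turn on the unresolved OPV question. Swaps within a group change nothing.

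**2. Mis-dosing at one visit only**

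One assigned dose is enough, so the child stays in. A Group 2 child given CAIV-T at Visit 1 and placebo at Visit 2 is counted as placebo for other adverse events after both doses.

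**3. How many children**

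Assume an error rate e per visit of 0.25% to 2%. This range is an assumption; the protocol gives none.

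- Visit 1 error carried to Visit 2: 2,400 × e = 2,400 × 0.0025 = 6, up to 2,400 × 0.02 = 48 with both doses wrong.
- Independent errors, both doses wrong: 2,400 × e² = 0.015 to 0.96.
- Independent errors, exactly one dose wrong: 2,400 × 2e(1 − e) = 11.97 to 94.08. These children stay in.

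The first two lines are ceilings for exclusion, because they count every wrong product, including swaps between Groups 1 and 3 that leave CAIV-T exposure unchanged. The carried-forward case follows from the sentence quoted above from Vaccine to be Administered. The Visit Two procedures instead call for the assigned intranasal product. For a child mis-dosed at Visit 1 the two passages differ and should be reconciled.

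**4. Effect on the comparison for children who stay in**

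Let D be the true difference in event proportion after a dose, a the fraction of the placebo group given CAIV-T, and b the fraction of the CAIV-T groups given placebo. Grouping by randomisation gives an expected difference of D × (1 − a − b).

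- a = b = 0.25%: 0.995 × D.
- a = b = 2%: 0.96 × D.

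For scale, the largest excess over placebo reported under Risks and Benefits is 11 points (runny nose or congestion after Dose One). That would become 11 × 0.995 = 10.945, or 11 × 0.96 = 10.56 points. This event is used only to show size, since the randomised-group wording is attached to other adverse events.

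**The case against.** The strongest reply is that the definition merely separates dosed children from those randomised but never dosed, a case that Randomisation Procedures foresees, and that handling of mis-dosed children belongs in the analysis plan. That is probably what the authors meant. But the protocol does not leave the matter open. It states a membership condition and a grouping, and an analysis plan that followed both literally would carry them over.

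It is also fair to say that the Study Visit One procedures treat the oral and intranasal products as separate assigned treatments. A Group 2 child given OPV as planned may therefore already qualify. That stands, and it narrows certain exclusion to swaps between Groups 2 and 3. If the child does qualify, however, the misclassification arises instead.

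A reader might infer three stronger things that the documents do not support:

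- *A mis-dosed child vanishes from every safety table.* The serious adverse event listing and the per-dose summary name no population, and all serious events are monitored throughout.
- *Both errors make the vaccine look safer.* Misclassification shrinks the difference. Exclusion removes the child from numerator and denominator alike and has no fixed direction. It would be related to outcome where a related serious event after a wrong first dose rules out a later assigned dose (Withdrawal criteria), but such an event is still covered by the listing.
- *Any child given another subject's allocation is lost.* Swaps within a group, or between Groups 1 and 3, leave an assigned dose in place.

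**Conclusion.** The point holds as a defect of stated wording. Taken literally, the definition leaves out a child whose entire course was non-assigned product, even if that product was CAIV-T. The adverse event comparison files mis-dosed children who remain under the product they did not receive. The second effect biases towards no difference; the first has no fixed direction.

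The expected size is small. Even 2% misclassification in both directions shrinks a difference by only 4% of its value. Wholly mis-dosed children number fewer than one if errors at the two visits are independent, and at most 6 to 48 if every Visit 1 error is carried forward. All of these figures rest on the assumed 0.25% to 2% error rate. Power and sample size are unaffected. The reason to act is that the change is simple and settles who counts before the code is opened.

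**What to change.** Define the Safety Population as all subjects who received at least one dose of any study vaccine or placebo (CAIV-T, intranasal placebo or OPV), analysed by the treatment actually received. In the comparison of other adverse events, replace *randomised to* with *who received*. Since events are summarised after each dose, group each dose period by the product given at that dose. The new definition also removes the question of whether OPV alone qualifies a child.

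The cost is two wording changes in the protocol, repeated in the analysis plan, with no new data: the vaccine accountability records already tie each administered dose to a subject. The downside is that, for the few mis-dosed children, the safety comparison no longer follows randomisation exactly.

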The data in Table 2 represent the cumulative total of subjects who experienced at least one episode of the symptom, irrespective of severity, during the 11 days of follow-up post-vaccination (Study Day 0 to Study Day 10) as obtained from worksheets completed by the parents or legal guardians. These are parental or legal guardian observations and did not involve pre-defined symptomatology.

No clinically pertinent differences can be observed between the rates of reactogenicity episodes in D153P500 for either study group and for either dose of the frozen or liquid formulations. The rates of respiratory symptoms following each dose were consistent between the two groups in D153P500, and importantly were also consistent with data summarised from Aviron clinical trials where approximately one-third of children aged 12 to 23 months experienced cough and 69% experienced runny nose or nasal congestion following receipt of CAIV-T 37; and in previously published observations in the 2 month old to 18 month old age group, where at least one-third experienced cough and 57% experienced runny nose or nasal congestion following receipt of bivalent influenza A CAIV, compared with a rate of 50% in placebo recipients 39.

Table 2
Study D153P500 Reactogenicity events with onset Day 0 to 10 by Dose and Treatment Group (All data blinded)—Children 12-36 months of age

Events	Post-dose 1		Post-dose 2	
	Group 1 (n=662)	Group 2 (n =658)	Group 1 (n=649)	Group 2 (n=649)
Cough	341 (52)	313 (49)	289 (45)	265 (42)
Runny nose/	478 (73)	445 (69)	371 (58)	363 (57)
Nasal congestion				
Sore throat	72 (11)	58 (9)	35 (6)	43 (7)
Irritability	147 (23)	150 (24)	97 (15)	90 (14)
Headache	77 (12)	63 (10)	47 (7)	34 (5)
Chills	32 (5)	33 (5)	26 (4)	20 (3)
Vomiting	78 (12)	74 (11)	55 (9)	44 (7)
Muscle aches	34 (5)	21 (3)	16 (3)	5 (1)
Decreased	88 (14)	49 (8)	44 (7)	38 (6)
Activity				
Fever $\geq 37.5^{\circ}\text{C}$	67 (11)	61 (10)	65 (10)	66 (11)
Fever $\geq 38.5^{\circ}\text{C}$	28 (5)	24 (4)	33 (5)	37 (6)
Fever $\geq 40.0^{\circ}\text{C}$	1 (0.2)	2 (0.3)	4 (0.6)	5 (0.8)
Any reactogenic event	553 (84)	522 (81)	443 (70)	439 (70)

Groups 1 and 2 received either frozen or liquid versions of CAIV-T. The designation remains blinded at this time. The numbers in parentheses represent percentage of subjects who experienced an episode.

Good Clinical Practice and Regulatory Compliance

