Each dose of intranasal CAIV-T or placebo will consist of approximately 0.2 ml in total volume administered as an intranasal spray using a spray applicator. Approximately 0.1 ml will be sprayed into each nostril. Details of the specific OPV to be used will be provided in the Investigator manual. OPV will be administered orally according to the manufacturer's instructions. Immediately following the vaccination each subject will be observed for 15 minutes for signs and symptoms of anaphylaxis and local reactions (e.g., nasal congestion/runny nose). The time interval between the assigned first dose and the assigned second dose will be 35 +/- 7 days. Prior to the second vaccination the subject will be assessed for continued eligibility.

A blood sample of approximately 5 millilitres will be collected from subjects on three occasions to evaluate immunogenicity using a serum hemagglutination inhibition assay for influenza virus types A/H1N1, A/H3N2 and B and a virus neutralisation assay for Polio types 1, 2, and 3. These blood samples will be collected prior to the first dose (study visit 1), prior to the second dose (study visit 2), and 35 +/- 7 days after the second dose (study visit 3). Specimen collection and processing guidelines will be provided separate from this document.

Following vaccination, field research assistants (FRAs) will visit each child at home for 11 consecutive days from the day of vaccination, Day 0 to Day 10, and collect data on axillary temperature, runny nose/nasal congestion, cough, vomiting, irritability, and decreases in appetite and activity level using a

standardised questionnaire. The FRA will then check the child's temperature with a digital thermometer supplied by WL.V. If the child has fever, elevated respiratory rate ($> 50/\text{min}$) or danger signs (chest indrawing, lethargy, unwillingness to feed, convulsion, or cyanosis), then the FRA will immediately refer them to clinic. Information regarding any physician consultations and any other concomitant medications (excluding fluoride supplements and vitamins) will also be recorded for 11 days after each vaccination. These children are presently under weekly surveillance for disease incidence (dengue, ALRI, diarrhoea). After the daily visits for 11 consecutive days, routine weekly surveillance will be resumed and all study participants will be advised when to visit the field clinic for their scheduled blood draw on day 35 ± 7 days post vaccination.

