Criteria for Temporarily Delaying Vaccination Administration

In general, the subject must be in good health (by physical examination and medical history) at the time of each study vaccination. The following conditions are temporary or self-limiting and a subject may receive study vaccine once the condition(s) has/have resolved and no other exclusion criteria are met:

- A febrile illness (axillary temperature > 37.5°C) or other acute illness within 36 hours prior to study vaccine administration.
- A respiratory illness in the subject and/or household member within 72 hours prior to study vaccine administration. Study vaccination of the subject may occur if a subject is experiencing mild symptoms of the common cold (e.g., slight cough and a runny nose), which is not going to be medically treated, and if the investigator feels that the subject's condition is not a respiratory illness and does not require any special clinical management. If the symptoms require medical intervention, it should be considered a respiratory illness and the study vaccination should be delayed until the illness has resolved. Vaccination should be delayed if a subject is taking medication (other than an antibiotic—see below) to prevent a particular respiratory related symptom (e.g., runny nose). In addition, if nasal blockage exists, it must be minimal enough to not reduce the likelihood of successful administration of the vaccine.
- Treatment of the subject with an antibiotic within 72 hours prior to study vaccine administration. Vaccination should be delayed if the subject requires any medical intervention with an antibiotic at the time of vaccination. If a subject is currently taking medicine (other than an antibiotic) at the time of vaccination for prophylaxis against a non-respiratory related illness, the subject may be vaccinated.
- Administration of any live virus vaccine (other than assigned study vaccine) within one month prior to enrolment or expected to receive another live virus vaccine (other than assigned study vaccine) within one month of vaccination in this study.
- Receipt of the third dose of the primary schedule of OPV within the 60 days prior to the first study vaccination.
- Receipt of any subsequent dose of OPV (a fourth or later dose) within 60 days prior to the first study vaccination.
- Receipt of a dose of any influenza treatment (commercial or investigational) in the two weeks prior to vaccination.

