The schedule of procedures for individual study participants is presented in Table 3. To ensure study visits are scheduled within the correct timeframes, the day of each vaccination visit should be considered as Day 0.

Study Screening Procedures

Prior to enrolment, the Investigator will review the subject's medical history to ensure that the subject is in good health and meets all of the inclusion criteria and none of the exclusion criteria.

Informed Consent

Informed written consent will be obtained in the privacy of study subject's home. The parent(s)/legal guardian(s) of subjects who fulfil all the study eligibility criteria will be informed of the purpose and conduct of the study and asked to read the information leaflet and consent form. Voluntary written study-specific informed consent will be obtained from the parent(s)/legal guardian(s) before any study-related procedures are performed. The parent(s)/legal guardian(s) must sign and date the consent form. □ The Investigator (or authorised designee listed on the Authorised Signature Record/Investigator Delegation Log) is responsible for obtaining written informed consent for each subject enrolled. Each signature on the informed consent form must be personally dated by the signatory. A copy of the signed and dated Informed Consent Form is given to the subject's parent(s)/ legal guardian(s). The subject's source documentation must reflect that informed consent was obtained prior to participation in the study. Following informed consent, baseline household demographic data will be updated and parent(s)/legal guardian(s) will be given a date and time to bring children to the field clinic for all procedures and vaccination.

Study Visit Procedures

Study Visit One, (Day 0)

-- Obtain and record medical history, including current medication usage and vaccination history (see section 6.2).

-- Perform physical examination, including axillary temperature, to determine that no acute illness is present.

If the subject continues to meet all of the inclusion criteria, *and* none of the exclusion criteria, assign the next sequentially-available subject identification number.

-- Collect approximately 5 ml of blood (before vaccination) for immunogenicity testing.

-- Administer a single dose of assigned study treatment see section 6. The appropriate study personnel must update the vaccine accountability records.

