Note: The assigned oral study treatment should be administered first (if applicable), with the assigned intranasal study treatment administered no more than 30 minutes later.

-- After vaccination, observe each subject for a minimum of 60 minutes. Emergency management supplies (AMBU bag, adrenaline (epinephrine), and antihistamines) will remain available for initial treatment of an allergic reaction if needed. (All medical personnel will have been trained on treatment procedures regarding emergency intervention for anaphylaxis.) Record any local reactions or systemic events on adverse event pages in the CRF.

-- Beginning that afternoon and for the following 10 days, daily axillary temperature and reactogenicity events will be captured on a standardised questionnaire by the FRAs. They will also record any other adverse events, unscheduled physician visits, concomitant prescription and non-prescription medication used.

-- The parent(s)/ legal guardian(s) will be asked to contact their FRA or the field clinic immediately if any significant illness or hospitalisation occurs during the study period.

-- Any subject with a clinically significant event (e.g., high fever, convulsion, etc) will be evaluated immediately by a study physician.

-- Serious adverse events (SAEs) data, regardless of causality, will be collected up to study completion. Treatment for such events will be provided by the study, including hospitalisation, at no cost to the study subject.

-- The subject and parent(s)/legal guardian(s) will be given an appointment to return for their next study visit.

-- Record all information in the appropriate source documents, and complete the CRF.

Study Clinic Visit Two, (Day 0)

This visit occurs 35 (+/- 7) days after the first dose of assigned study vaccine. Surveillance staff will visit the home prior to the scheduled visit to remind the parent.

-- Review patient information from previous visit. Obtain and record interim medical history including all adverse events and concomitant medications between Day 0 and Day 10 following the first dose of assigned study treatment (see section 6.2).

-- Assess subject to ensure continued study eligibility. Record axillary temperature, to determine that no acute illness is present.

If the subject continues to meet the study eligibility criteria:

-- Collect approximately 5 ml of blood for immunogenicity testing.

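### Reactogenicity is counted on any report from Day 0 to Day 10 with no onset condition, although children may be dosed with mild cold symptoms, so some pre-existing cough and runny nose will be scored as reactions

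*Protocol*

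**What the plan says.** The Data Analysis section lists seven reactogenicity adverse events: "Fever (axillary temperature > 37.5°C); Cough; Runny nose or nasal congestion; Irritability; Vomiting; Decreased activity; and Decreased appetite". What will be evaluated is "The proportion of subjects with any reactogenicity event reported and with other adverse events on any day during the 11-day period following each dose". No condition on onset, worsening or change from pre-dose status is attached. Groups are compared by two-sided Fisher's exact test, with exact 95% confidence intervals for the differences.

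Under Research Design and Methods, field staff "visit each child at home for 11 consecutive days from the day of vaccination, Day 0 to Day 10". Under Study Visit One, the timing is: "Beginning that afternoon and for the following 10 days, daily axillary temperature and reactogenicity events will be captured on a standardised questionnaire by the FRAs".

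The section on criteria for temporarily delaying vaccination applies at each dose. It delays dosing for a respiratory illness, but dosing may go ahead "if a subject is experiencing mild symptoms of the common cold (e.g., slight cough and a runny nose" are its examples), provided the symptoms will not be medically treated and the investigator judges that this is not a respiratory illness. Fever is handled differently. A listed reason for delay is "A febrile illness (axillary temperature > 37.5°C) or other acute illness within 36 hours prior to study vaccine administration".

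Before Dose 1, staff take a medical history and "Perform physical examination, including axillary temperature, to determine that no acute illness is present". Before Dose 2, they take an interim history, check continued eligibility and record temperature; Table 3 schedules no physical examination at that visit. Neither visit calls for the symptom questionnaire to be completed before the dose.

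**The concern.** Two of the symptoms that the endpoint counts are the same two that the dosing rule tolerates. A child who arrives with a slight cough or runny nose, is dosed, and still has it at a home visit meets the counting rule as written, whichever product was given.

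Randomisation spreads such children evenly in expectation, so they add the same number of cases to each group. They cannot create a difference, but they make a real one look smaller and push up every reported rate. In a safety comparison that is the unwelcome direction: an excess of respiratory symptoms is understated. For a live intranasal vaccine these symptoms matter most. The Risks and Benefits section gives runny nose/nasal congestion the largest excess over placebo after Dose 1, 11 points.

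This is not merely detail left to a later plan. A statistical analysis plan can add an onset rule, but it could not fully rebuild an item-level pre-dose record that nobody was asked to collect.

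**Working it through.** **The plan's own figure.** The protocol states no power for reactogenicity. Its stated 98% is for each immunogenicity comparison (55% v 55%, margin 10 points, one-sided 0.05, 680 completers per group). It reproduces: SE = √(2 × 0.55 × 0.45 / 680) = 0.0270; 0.10/0.0270 − 1.645 = 2.06; power 98.0%. Also 800 × 0.85 = 680, which confirms 800 per group. Nothing below depends on the 98%.

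**Inputs.**
- 800 per group: study group table. Group 2 is the only group given intranasal placebo.
- Runny nose or congestion 57% v 50% placebo: Background, the comparison of frozen and liquid formulations, for a bivalent vaccine at 2 to 18 months. Taken here as new-onset risks, which is an assumption.
- 11-point excess for runny nose/congestion after Dose 1: Risks and Benefits, frozen formulation. A 50% placebo rate is assumed with it.
- Two-sided alpha 0.05: assumed; the protocol gives none for this test.
- p0, the proportion with the symptom before the dose: not in the protocol; 5% to 30% assumed.

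**Formula.** Let p be the new-onset risk in children free of the symptom, and suppose every child with it before the dose is reported with it afterwards. The rate seen in a group is P = p0 + (1 − p0)p. Subtracting one group from the other, p0 cancels and the difference seen is (1 − p0) × (true new-onset difference). If some symptoms clear before the first afternoon visit, the dilution is less.

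**Power** uses the normal approximation (pooled variance under the null, unpooled under the alternative). Worked case at p0 = 20%: placebo 0.20 + 0.80 × 0.50 = 0.600; CAIV-T 0.20 + 0.80 × 0.57 = 0.656; difference 0.056. Then (0.056 − 1.96 × 0.02417)/0.02413 = 0.36, so power is 64%. The new-onset analysis uses 800 × (1 − p0) children per group at 57% v 50%.

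| p0 | Placebo seen | CAIV-T seen | Difference seen (points) | Power, any report | Same, simulated Fisher test | Power, new onset only |
|---|---|---|---|---|---|---|
| 0 | 50.0% | 57.0% | 7.0 | 80% | 79% | 80% |
| 5% | 52.5% | 59.15% | 6.65 | 76% | 75% | 78% |
| 10% | 55.0% | 61.3% | 6.3 | 72% | 72% | 76% |
| 20% | 60.0% | 65.6% | 5.6 | 64% | 62% | 71% |
| 30% | 65.0% | 69.9% | 4.9 | 55% | 53% | 65% |

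**Larger effect.** With 11 points over the assumed 50%, the difference seen is 10.5, 9.9, 8.8 and 7.7 points at p0 = 5, 10, 20 and 30%. Power goes from 99% to 99, 98, 96 and 92% (99, 99, 98 and 96% on new onset only). Here the estimate suffers more than the test.

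**Type I error.** With equal true risks, the simulated Fisher test rejected in 4.4%, 5.2% and 4.3% of 4,000 runs at p0 = 0, 10 and 30%. There is no inflation.

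**The case against.** The best opposing case has five parts.

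- *Some pre-dose information exists.* History, the Visit 1 examination and the eligibility check all touch on it, and the delay rule cannot be applied without looking for cough, runny nose and blockage. This stands: a reader might infer that nothing at all is known before the dose, and that is too strong. What is missing is an item-by-item record and a rule that uses it. The weekly home surveillance does not fill the gap, because it is described for Bangladesh only and is not tied to the endpoint.
- *The permission is narrow.* Symptoms must be mild, untreated and judged not to be a respiratory illness, and a respiratory illness in the child or household within 72 hours delays dosing. This stands, and it argues against a very high p0.
- *The questionnaire and analysis plan are not shown.* They may handle ongoing symptoms. Hence the point is that such symptoms can be scored as reactions, not that every child with a cold will be. The protocol's own wording nevertheless rests the count on reporting.
- *No decision hangs on it.* Reactogenicity has no margin, powered hypothesis or pass/fail rule. True, but the estimates and intervals are the safety result, and they are what is diluted.
- *Judging whether a symptom got worse is subjective.* Only Groups 1 and 2 are blinded to the intranasal product. This stands and shapes the fix.

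A reader might also infer that an onset safeguard used in the sponsor's earlier trial was deliberately dropped, because Table 2 is captioned "Reactogenicity events with onset Day 0 to 10 by Dose and Treatment Group". The documents do not support that. The text introducing the table describes the same data as subjects with at least one episode during the 11 days, with no onset condition. Caption and text may be two descriptions of one rule.

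**Conclusion.** The concern holds in a limited form. The counting rule and the dosing rule overlap, and the protocol schedules no structured pre-dose symptom record with which to separate them. The effects are inflated absolute rates and a between-group difference multiplied by (1 − p0) for cough, runny nose/congestion and the any-event composite. Fever is largely unaffected because of the 36-hour rule.

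The factor is exact under the stated formula; its size is not known, because p0 is not in the protocol. For 57% v 50% and p0 of 5% to 30%, the loss is 0.35 to 2.1 points out of 7.0, and power is 76% to 55% instead of 80%. If p0 is low, the effect is small.

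Two stronger conclusions should not be drawn. First, the whole power loss is not due to the definition: children already symptomatic cannot show a new onset, so the change recovers about 2 points of power at p0 = 5% and 10 at 30%. Its main gain is the undiluted estimate. Second, the comparison is not invalid: type I error is kept, and the primary immunogenicity objectives are untouched.

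**What to change.** At Visits 1 and 2, immediately before the dose, record each of the seven solicited symptoms as present or absent. In the Data Analysis section, define a new-onset event as a symptom absent before that dose and reported on any of Days 0 to 10, and compare new-onset events between groups. Report the any-report rate alongside it. A worsened-from-baseline count, if wanted, should be secondary only, since it needs a judgement and Group 3 is not blinded. No dosing rule changes.

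The cost is one short checklist per dose, at visits where history and temperature are already taken, and a reworded endpoint. Children who already have a symptom leave that symptom's new-onset count. The checklist must be in place before enrolment starts, because the pre-dose status cannot be fully reconstructed afterwards.
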